TITLE PAGE

Division: Worldwide Development

Information Type: Worldwide Epidemiology Study Protocol

Title:	Drug Utilization of Pirinase Hayfever Relief for Adults 0.05% Nasal Spray for Allergic Rhinitis Symptoms in Adults
---------------	---

Compound: Fluticasone propionate

Development Phase Post Authorization Study

Effective Date: 15-02-2016

Subject: Seasonal Allergies

Author(s): PPD

Copyright 2016 the GlaxoSmithKline group of companies. All rights reserved.
Unauthorised copying or use of this information is prohibited

PASS information

Title	Drug Utilization of Pirinase Hayfever Relief for Adults 0.05% Nasal Spray for Allergic Rhinitis Symptoms in Adults
Protocol version identifier	3.0
Date of last version of protocol	08 March 2016
EU PAS (ENCEPP) register number	EUPAS12436
Active substance	Fluticasone propionate Pharmacotherapeutic group: Intranasal Corticosteroids ATC Code: R01AD08
Medicinal product	Pirinase Hayfever Relief for Adults 0.05% Nasal Spray
Product reference	PL 00079/0688
Procedure number	N/A
Marketing authorisation holder(s)	Beecham Group Plc [name] Trading as GlaxoSmithKline Consumer Healthcare, [name]
Joint PASS	No

Research question and objectives
	
The primary objective of this study is to evaluate if consumers comply with key warnings and directions on the outer label for selection and use of the drug.
 
Primary Objectives
 
The five primary objectives are the following:
 
 1. To assess if consumers of the correct age use the product: Ages 18 and older 2. To assess the correct frequency of use: No more than 2 sprays in each nostril per day 3. To assess reduction of dose: If symptoms improve, 1 spray in each nostril per day 4. To assess if a physician is consulted before use: if a woman is pregnant or breastfeeding 5. To assess if a physician is consulted: If symptoms have not improved after using for 7 days, a doctor is consulted 
Secondary Objectives
 
The two secondary objectives are the following:
 
 1. To assess if consumers do not use if they are taking medications for Human Immunodeficiency Virus (HIV) 2. To assess if a physician is consulted: Not used more than 1 month continuously without consulting a doctor

Country of study
	
United Kingdom

2. ABSTRACT

Title

Drug Utilization Study for Pirinase Hayfever Relief for Adults 0.05% Nasal Spray

Rationale and background

The Medicines and Healthcare products Regulatory Agency (MHRA) has required this study to evaluate consumer compliance with the product labelling of Pirinase Hayfever Relief for Adults 0.05% Nasal Spray over at least 2 allergy seasons for the treatment of seasonal allergic rhinitis including hayfever. The purpose is to obtain real-world information on how consumers are complying with the product labelling. This study will coincide with the launch of Pirinase Hayfever Relief for Adults 0.05% Nasal Spray in the United Kingdom (UK).

Research question and Objectives

The primary objective of this study is to evaluate if consumers comply with key warnings and directions on the outer label for selection and use of the drug.

Study Objective

To evaluate if consumers comply with key warnings and directions on the outer label for selection and use of the drug

Primary Objectives

The five primary objectives are the following:

1. To assess if consumers of the correct age use the product: Ages 18 and older
2. To assess the correct frequency of use: No more than 2 sprays in each nostril per day
3. To assess reduction of dose: If symptoms improve, 1 spray in each nostril per day
4. To assess if a physician is consulted before use: if a woman is pregnant or breastfeeding
5. To assess if a physician is consulted: If symptoms have not improved after using for 7 days, a doctor is consulted

Secondary Objectives

The two secondary objectives are the following:

1. To assess if consumers do not use if they are taking medications for Human Immunodeficiency Virus (HIV)
2. To assess if a physician is consulted: Not used more than 1 month continuously without consulting a doctor

Study Design

This will be an online survey. Consumers who have purchased and used the product will opt into an online survey by scanning a QR code on the product package labelling or through an e-mailed invitation to those who have purchased the product at a Boots Pharmacy, which will also include a link to the survey. The anticipated study timeframe is approximately 2 calendar years so that data from at least 2 allergy seasons for the treatment of seasonal allergic rhinitis including hayfever are included. The intention will be to recruit approximately half the subjects in each year.

Population

An all comers population (consumers who opt in at their own discretion) of 1,537 consumers, will be included in this study. No targeting or enrichment for age, gender, and social backgrounds will be conducted. The demographics will be reported for those who choose to enter the online survey

Variables

Primary endpoints are comprised of the proportion of consumers who comply with each of the 5 endpoints listed below:

1. Consumer is 18 years of age or older
2. Consumer does not exceed 2 sprays/nostril per day
3. Dose is reduced to 1 spray/nostril per day if symptoms improve
4. Doctor is consulted before use if a woman is pregnant or breastfeeding
5. Doctor is consulted if symptoms do not improve after 7 days of use

Secondary endpoints are comprised of the proportion of consumers who comply with each of the specified endpoints below:

1. Those taking HIV medications do not use the drug
2. Doctor is consulted is medication is used more than 1 month *continuously*

Demographics and Profiling Information

Descriptive statistics will be used to report consumer demographics and additional profiling information. Demographic information is comprised of age, race, education and household purchase information (primary purchaser or other). The additional profiling information is comprised of the following:

- How long they have had allergies
- What type of allergies they have
- Typical allergy symptoms
- How often they see their doctor

Data Sources

Endpoints will be assessed based on data from self-reported consumer responses to the online survey.

Study Size

1,537 consumers will complete the survey. No targeting or enrichment for age, gender, and social backgrounds will be conducted. The demographics will be reported for those who choose to enter the online survey. For the threshold of 80% for success, this sample size of 1537 achieves at least 91% power with an assumed compliance rate of 83.3% for each of these five primary endpoints, and the significance level of 0.05 using a two-sided exact binomial test.

Data Analysis

Primary endpoints will be analyzed individually and no adjustment for multiple comparisons will be performed. The compliance rate for each of the five primary endpoints will be reported and its two-sided 95% confidence limit will be computed using the exact method. The endpoint will have met the threshold for success if the lower bound of the 2-sided 95% exact confidence interval (CI) is at least 80%.

Secondary endpoints will be analyzed individually and no adjustment for multiple comparisons will be performed. The compliance rate for each of the secondary endpoints will be reported and its two-sided 95% confidence limit will be computed using the exact method. There are no success thresholds set for secondary endpoints.

Milestones

Milestones for this study include the following:

1. Start of data collection February 2016
2. Study progress report February 2017
3. End of data collection March 2018
4. Final report of study results June 2018

3. AMENDMENTS AND UPDATES

Amendment or update no	Date	Section of study protocol	Amendment or update	Reason
1	02MAR2016	8.8	Added in limitations of the research methods	MHRA request

2	08MAR2016	8.8	Added in additional limitation of the research methods	MHRA request
---	-----------	-----	--	--------------

4. MILESTONES

Milestone	Planned date
Start of data collection	February 2016
End of data collection	March 2018
Study progress report 1*	February 2017
Final report of study results	June 2018

* An enrolment update will be submitted to MHRA after approximately 1 year of enrolment. No interim data analysis is planned.

5. RATIONAL AND BACKGROUND

5.1. Background

The Medicines and Healthcare products Regulatory Agency (MHRA) has required a post-approval commitment from GlaxoSmithKline Consumer Healthcare (GSKCH) for Pirinase Hayfever Relief for Adults 0.05% Nasal Spray. This spray will be marketed for General Sale (GSL) in the United Kingdom (UK).

5.2. Rationale

The post-approval commitment to MHRA is to provide observational data regarding the real-world use of Pirinase Hayfever Relief for Adults 0.05% Nasal Spray by consumers. Specifically, data about the consumer’s compliance with key warnings and directions will be collected.

6. RESEARCH QUESTION AND OBJECTIVE(S)

The primary objective of this study is to evaluate if consumers comply with key warnings and directions on the outer label for selection and use of the drug.

The primary and secondary objectives and endpoints are listed below:

Primary Objectives	Primary Endpoints
---------------------------	--------------------------

 To assess if consumers of the correct age use the product: Ages 18 and older 	
 Consumer is 18 years of age or older

 To assess the correct frequency of use: No more than 2 sprays in each nostril per day 	
 Consumer does not exceed 2 sprays/nostril per day

 To assess reduction of dose: If symptoms improve, 1 spray in each nostril per day 	
 Dose is reduced to 1 spray/nostril per day if symptoms improve

 To assess if a physician is consulted before use: if a woman is pregnant or breastfeeding 	
 Doctor is consulted before use if a woman is pregnant or breastfeeding

 To assess if a physician is consulted: If symptoms have not improved after using for 7 days, a doctor is consulted. 	
 Doctor is consulted if symptoms do not improve after 7 days of use

Secondary Objectives	Secondary Endpoints

 To assess if consumers do not use if they are taking medications for Human Immunodeficiency Virus (HIV)] 	
 Those taking HIV medications do not use the drug

 To assess if a physician is consulted: Not used more than 1 month continuously without consulting a doctor 	
 Doctor is consulted if medication is used more than 1 month continuously

Demographic information that will be collected are listed below:

1. Age
2. Race
3. Education
4. Primary purchaser of medicines

Additional profiling information that will be collected are listed below:

1. How long they have had allergies
2. What type of allergies they have
3. Typical allergy symptoms
4. How often they see their doctor

6.1. Study Design

This is an online survey to evaluate consumer compliance with the product labelling for consumers who purchase Pirinase Hayfever Relief for Adults 0.05% Nasal Spray. Consumers will respond to screening criteria and if they qualify for the study, they will complete the online survey related to their use of the drug. After completing the survey consumer participation will be considered complete. Data collection will continue through at least 2 allergy seasons and until 1,537 surveys are completed.

Consumers will access an online survey by scanning a QR code on the product package labelling or through an e-mailed invitation to those who have purchased the product at a Boots Pharmacy, which will also include a link to the survey. The entire study will be conducted online; there will be no study visits.

The specific tasks include the following:

- 1) Consumers who have purchased the product will scan the QR code found on the product package labelling or by accessing the link in the e-mailed invitation.
- 2) A Participation Agreement will be displayed. The consumer will read and sign this Agreement electronically. Anyone who does not sign the Participation Agreement will not be admitted to the survey.
- 3) The online survey will begin with a set of brief screening questions related to the inclusion/exclusion criteria.
- 4) If the consumer qualifies and is interested, he or she will then be invited to complete the online survey. This process is voluntary for all participants.
- 5) The online survey will consist of closed-ended questions related to the consumer's use of the product.
- 6) Demographics and profiling information will be collected.
- 7) If a consumer has not used the product for at least a month when they initially complete the survey, a reminder message will be sent to them at a later time so that they can complete the question related to use after 1 month.
- 8) After completing the survey, consumer participation in the study will be considered complete.

7. SCHEDULE OF EVENTS

Procedure / Assessment	Initial Survey Response Day	Subsequent Survey Response Day ²
Inclusion / Exclusion Criteria	X	
Participation Agreement	X	
Online compliance survey completion	X	
Self-reported demographics	X	
Self-reported allergy profiling information	X	
Reminder message sent to consumers who have not used the product for at least 1 month at the initial response day ¹		X
Self-reported compliance with 1 month warning ¹	X	X
Study conclusion	X	

¹

Label Warning: To assess the correct frequency of use (not used more than 1 month continuously without consulting a doctor).

²

Subsequent Survey Response Day: This is for consumers who had not used the product for at least 1 month when they initially completed the survey. This allows subject to complete the 1 month question on the survey.

7.1. Study Population and Setting

1,537 consumers in the UK who have purchased and used Pirinase Hayfever Relief for Adults 0.05% Nasal Spray for at least 7 days will be included in this study. No targeting or enrichment for age, gender, and social backgrounds will be conducted. The demographics will be reported for those who choose to enter the online survey.

The anticipated timeframe is approximately 2 calendar years so that data from at least 2 allergy seasons for the treatment of seasonal allergic rhinitis including hayfever are included. The allergy season in the UK can range from April through September with June often having the highest pollen counts and allergy sales; however, allergy seasons vary. If the sample size is not met within the 2-year period the study may be extended.

This is an all comers study which means that consumers will opt into the survey themselves. Consumers will access the online survey by scanning a QR code on the product package labelling or through an e-mailed invitation to those who have purchased the product at a Boots Pharmacy, which will also include a link to the survey. The population is expected to reflect a real-world population of consumers who will purchase and use the drug.

Inclusion:

A consumer will be eligible for inclusion in this study only if all of the following criteria apply:

1. Consumers will be required to review, and electronically sign a Participation Agreement prior to completing the online survey.
2. Consumers of any age may participate.
3. Consumers who have purchased and used Pirinase Hayfever Relief for Adults 0.05% Nasal Spray for at least 7 days and are willing to participate in the online survey.
4. Consumers of either gender may participate

Exclusion:

A consumer will not be eligible for inclusion in this study if any of the following criteria apply:

1. Anyone who is directly involved with medicines such as doctors, nurses, and pharmacists.
2. Consumers who decline participation in the online survey

7.2. Variables

7.2.1. Outcome definitions

Primary Endpoints

Primary endpoints are comprised of the proportion of consumers who comply with each of the 5 endpoints listed below:

- Consumer is 18 years of age or older
- Consumer does not exceed 2 sprays/nostril per day
- Dose is reduced to 1 spray/nostril per day if symptoms improve
- Doctor is consulted before use if a woman is pregnant or breastfeeding
- Doctor is consulted if symptoms do not improve after 7 days of use

Secondary Endpoints

Secondary endpoints are comprised of the proportion of consumers who comply with each of the specified endpoints listed below:

- Those taking HIV medications do not use the drug
- Doctor is consulted if medication is used more than 1 month *continuously*

Demographics and Profiling Information

Descriptive statistics will be used to report consumer demographics and additional profiling information. Demographic information is comprised of age, race, education and household purchase information (primary purchaser or other). The additional profiling information is comprised of the following:

- How long they have had allergies
- What type of allergies they have
- Typical allergy symptoms
- How often they see their doctor

7.3. Data sources

Endpoints will be assessed based on data from self-reported consumer responses to the online survey.

7.4. *Study size

1,537 consumers will complete the survey. No targeting or enrichment for age, gender, and social backgrounds will be conducted. The demographics will be reported for those who choose to enter the online survey. For the threshold of 80% for success, this sample size of 1537 achieves at least 91% power with an assumed compliance rate of 83.3% for each of these five primary endpoints, and the significance level of 0.05 using a two-sided exact binomial test.

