7.8. Limitations of the research methods

7.8.1. Limitations

This study will be conducted as an online survey and will be limited to only those who have access to the internet. Since internet usage is correlated to various demographics,

the age and gender of those who enrol could be slightly different from the general population. Also due to only being an online survey, baseline characteristic of those who are able to enrol could potential be different from those who do not have internet access and cannot enrol. This might limit the external validity of the study.

Consumers who have not used the product for greater than 1 month will be able to complete all of the survey except the questions around the 1 month usage. They will be invited back after they have had the opportunity to use the product for one month to complete the 1 month usage questions. There is a possibility that some of these consumers will not re-enter the survey after 1 month to complete those questions. Data for the secondary objective of *doctor is consulted if medication is used more than 1 month continuously* may be limited.

Given that there are approximately 100,000 HIV+ patients in the UK¹ and the proposed sample size for this study of 1,537, it is unlikely that consumers on HIV medications will complete the survey. Data for the secondary objective of *those taking HIV medications do not use the drug* may be limited.

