## 2. STUDY ENDPOINTS

### 2.1.1 Primary Endpoints

Primary endpoints are comprised of the proportion of consumers who comply with each of the five primary objective endpoints, namely:

1. Proportion of consumers with 18 years of age or older.
2. Proportion of consumers who don't exceed 2 sprays/nosetril per day.
3. Proportion of consumers whose dose is reduced to 1 spray/nosetril per day if symptoms improve.
4. Proportion of female consumers who consulted a Doctor before using the drug if pregnant or breastfeeding.
5. Proportion of consumers who consulted a Doctor if symptoms did not improve after 7 days of use.

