### 3. SAMPLE SIZE AND STATISTICAL POWER CONSIDERATIONS

1,537 consumers were planned to complete the survey. No targeting or enrichment for age, gender, and social backgrounds will be conducted. The demographics will be reported for those who choose to enter the online survey. For the threshold of 80% for success, this sample size of 1537 achieves at least 91% power with an assumed compliance rate of 83.3% for each of these five primary endpoints, and the significance level of 0.05 using a two-sided exact binomial test.

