### 4.5 PRIMARY ANALYSES

Primary endpoints (defined in Section 2.1.1) will be analyzed individually in full analysis set, and no adjustment for multiple comparisons will be performed. The compliance rate

for each of the five primary endpoints will be reported and its two-sided 95% confidence limit will be computed by using the Clopper-Person exact method. The endpoint will have met the threshold for success if the lower bound of the 2-sided 95% exact confidence interval (CI) is at least 80%.

Listing of consumers for each of primary endpoints will be reported in full analysis set.

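### The 91% power claimed for all five primary endpoints holds only for endpoints 1 and 2; it cannot hold for endpoint 4, nor plausibly for both 3 and 5

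*Protocol*

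**What the plan says.** Protocol 7.4 plans on the basis that "1,537 consumers will complete the survey" and computes one power figure at that number, for a two-sided exact binomial test at the 0.05 level against an 80% threshold. It applies the figure to every primary endpoint: the sample "achieves at least 91% power with an assumed compliance rate of 83.3% for each of these five primary endpoints". The abstract repeats this, and so does SAP 3: "this sample size of 1537 achieves at least 91% power with an assumed compliance rate of 83.3% for each of these five primary endpoints".

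Under SAP 4.5, each endpoint is analysed separately in the full analysis set and has "met the threshold for success if the lower bound of the 2-sided 95% exact confidence interval (CI) is at least 80" per cent.

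By their wording in Protocol 7.2.1 and SAP 2.1.1, the five primary endpoints do not all concern the same people:

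- Endpoints 1 (adult age) and 2 (daily spray limit) concern every respondent.
- Endpoint 3 (dose reduction) concerns consumers whose symptoms improve.
- Endpoint 4 is the "Proportion of female consumers who consulted a Doctor before using the drug if pregnant or breastfeeding".
- Endpoint 5 is "Doctor is consulted if symptoms do not improve after 7 days of use".

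Protocol 7.1 describes an all-comers sample without enrichment, in which "Consumers of either gender may participate". Neither document gives a denominator, an expected subset size or a power figure for endpoints 3 to 5.

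Protocol 7.8.1 warns of sparse data only for the two secondary endpoints. For the first of these it says that "it is unlikely that consumers on HIV medications will complete the survey".

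**The concern.** Power depends on the number evaluable as well as on the assumed compliance rate. The power sentence fixes that number at 1,537 for all five endpoints, although three of them are defined on subsets. Endpoint 4 can draw only on women who are pregnant or breastfeeding. The conditions for endpoints 3 and 5 are largely opposed, so a large group for one tends to mean a small group for the other.

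The MHRA required this study and would read the plan as giving every primary endpoint at least a 91% chance of passing at 83.3% compliance. If endpoint 4 misses, or endpoint 5 misses because few consumers fail to improve, the miss may reflect only a small denominator. A reader relying on the stated power would take it as evidence of poor compliance with the warning. Neither document flags this or says how to read such a result. For endpoint 3 the loss is small if nearly everyone improves.

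**Working it through.** **Inputs.** N = 1,537, assumed compliance p = 0.833, threshold 0.80 and two-sided 0.05 come from Protocol 7.4 and SAP 3. The Clopper-Pearson success rule comes from Protocol 7.6.1 and SAP 4.5. Subset sizes appear in neither document, so those used in step 5 are assumptions.

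**Method.** The critical count c(n) is the smallest x whose Clopper-Pearson lower 95% limit is at least 0.80. Power is P(X ≥ c(n)) for X ~ Binomial(n, p).

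**1. The plan's own figure.** At n = 1,537, 1,260 successes give a lower limit of 0.7996 and 1,261 give 0.8003, so c = 1,261. Power at p = 0.833 is 0.9114. The stated 91% reproduces.

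**2. How many evaluable consumers 91% needs.** Exact power is saw-toothed in n. It first rounds to 91% (≥ 0.905) at n = 1,482 and first reaches 0.910 at n = 1,514 (c = 1,242, power 0.9113). Between these, n = 1,509 gives 0.9098. Roughly 1,510 of the 1,537 are therefore needed.

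**3. Endpoint 4.** Even on the looser cut-off, 1,482/1,537 = 96.4% of respondents would have to be pregnant or breastfeeding women. An unenriched sample of either gender rules that out without any outside prevalence figure.

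**4. Endpoints 3 and 5.**

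- *Groups that do not overlap.* Over all splits of 1,537, the best achievable power for the weaker endpoint is 0.640, at 754/783.
- *Overlapping groups.* A consumer who improves only after day 7 could count in both. If each endpoint needs m consumers, the overlap must be at least 2m − 1,537. With m = 1,482 this is 1,427 (92.8%); with m = 1,514 it is 1,491 (97.0%).
- *Endpoint 3 alone* could come close to 91% if nearly all improve.

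**5. Power at illustrative denominators** (assumed shares of 1,537; a dash means not calculated here).

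| n (share) | c(n) | p = 0.833 | p = 0.90 | p = 0.95 |
|---|---|---|---|---|
| 1,383 (90%) | 1,136 | 88% | – | – |
| 1,230 (80%) | 1,012 | 84% | – | – |
| 768 (50%) | 637 | 63% | – | – |
| 307 (20%) | 260 | 29% | 99.9% | – |
| 154 (10%) | 134 | 13% | 91% | – |
| 77 (5%) | 69 | 9% | 64% | 98.5% |
| 46 (3%) | 43 | 4% | 31% | 80% |
| 16 (1%) | none | 0% | 0% | 0% |

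The last row follows because 16/16 has a lower limit of 0.794. The smallest n that can pass is 17, where 17/17 gives 0.805.

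**6. What a miss would mean.** Three outcomes are possible: success, an interval wholly below 80%, or an interval that includes 80% without meeting the rule.

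| n | Success needs | Interval wholly below 80% at | P(neither), p = 0.833 |
|---|---|---|---|
| 307 | 260 | 231 or fewer (upper limit 0.7997) | 71% |
| 154 | 134 | 112 or fewer (0.7958) | 87% |
| 77 | 69 | 53 or fewer (0.7891) | 91% |
| 46 | 43 | 30 or fewer (0.7865) | 96% |
| 16 | not attainable | 8 or fewer (0.7535) | 99.8% |

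**7. Counting everyone in the denominator.** Suppose consumers to whom a direction does not apply were scored as compliant, so that n stays at 1,537. Endpoint 4 would then pass with no consultation at all as long as no more than 1,537 − 1,261 = 276 women (18.0%) were pregnant or breastfeeding. It would no longer measure its objective.

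**The case against.** - **Endpoints 1 and 2 have no slack either.** The full analysis set is not defined as 1,537 completers, missing answers are excluded (SAP 6), and Protocol 7.5.1 lets the sponsor end data collection early. Power is 90.5% at n=1,500 and 90.95% at n=1,538. This stands as a qualification: the 91% is secure for these two endpoints on the plan's own premise of 1,537 completed surveys with forced answers. The replacement text should state that premise as a condition.
- **Denominators may be set elsewhere.** SAP 7 and 8 defer derivation rules and table shells to separate documents. That is possible, but no specification can make a conditional subset equal 1,537, and step 7 shows what scoring non-applicable consumers as compliant would do.
- **The shares for endpoints 3 and 5 are unknown, and the groups can overlap.** This is correct. The 64% ceiling applies only to disjoint groups, which is why the conclusion for this pair is that the claim is implausible for both, not impossible.
- **The practical effect is limited.** Exact intervals are already required, so imprecision will be visible, and at 90% true compliance n=154 gives 91% power. Both points are true. But the plan's claim is made at 83.3%, and at 90% compliance n=46 still gives only 31%.

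**Conclusion.** The power statement is wrong as written in all three places. It is right for endpoints 1 and 2, provided all 1,537 are evaluable and true compliance is 83.3%. It cannot be right for endpoint 4. It could be right for both 3 and 5 only if about 93% to 97% of respondents fell in both groups.

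The need for about 1,510 evaluable consumers and the 64% ceiling for disjoint groups rest on no assumed share. Power at particular subset sizes does rest on assumed shares and should be read as a range. The conclusion takes the conditional endpoint wording at face value. This must be corrected, because it concerns the stated power of primary endpoints that carry a pass/fail threshold.

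**What to change.** **Protocol 7.4, abstract and SAP 3.** Replace the power sentence with text such as:

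> For endpoints 1 and 2, if all 1,537 consumers are evaluable, power is at least 91% when true compliance is 83.3% (threshold 80%, two-sided exact test, significance level 0.05). Endpoints 3 to 5 are assessed in those members of the full analysis set to whom the direction applies. That number is not known in advance, and power depends on it. Illustrative values at 83.3% compliance, not expected numbers: about 88% at n=1,383, 63% at n=768, 29% at n=307, 13% at n=154, 9% at n=77, 4% at n=46, and 0% at n of 16 or fewer.

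**SAP 2.1.1 and 4.5.** State the denominators: for endpoint 3, consumers whose symptoms improved; for endpoint 4, women who were pregnant or breastfeeding; for endpoint 5, consumers not improved after 7 days of use. Say that one consumer may count in both 3 and 5, and keep the separate derivation specifications consistent with this.

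**Protocol 7.8.1.** Add that endpoint 4, and endpoint 5 if few fail to improve, may have too few consumers to meet the threshold even with high compliance.

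**SAP 4.5.** Add that each result is reported with its n and exact 95% interval. A missed threshold is inconclusive when the interval includes 80%, and is evidence of compliance below 80% when the upper limit lies below 80%.

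**Cost.** These are text changes only, with no extra enrolment and no change to the sample size or success criterion. The one drawback is a less favourable stated power for endpoints 3 to 5.
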